10.25.2 Study Completed

At the completion of the 24-Month Visit, subjects will be exited from the study. The 24-Month Visit and exit visit should be combined, and both a 24-Month Visit CRF and a Study Exit CRF need to be completed.

10.25.3 Lost to Follow-up

A subject is considered to be lost to follow-up if at least two attempts to contact the subject are unsuccessful. The method of attempt (e.g., one letter and one phone record, or two letters) must be documented in the subject's medical record. In addition, regulation set forth by the governing EC must be followed.

11. Risks and Benefits

11.1 Potential Risks

Medtronic follows rigorous Quality Assurance and Control procedures throughout the life of a product, from the business analysis phase through development, market release, and post-market surveillance. The risk analysis process for the Inceptiv system is being performed in accordance with ISO 14971, and will ensure that the level of risk is as low as possible prior to starting the study.

It is anticipated there are no incremental risks introduced to the subject as a result of participation in this study or with the implantation of the Inceptiv system. Any new identified risks will be communicated to Investigators and result in a CIP revision.

11.2 Foreseeable Risks

11.2.1 SCS Adverse Events Summary

The implantation of a SCS system involves risks that are similar to other spinal cord procedures. In addition to those risks associated with surgery, the following adverse events may occur with implantation or uses of a neurostimulation system.

- Allergic or immune system response to the implanted materials
- Infection
- Lead, extension, or neurostimulator erosion through the skin or migration
- Leakage of cerebrospinal fluid
- Loss of pain relief may return patients to their underlying pain condition
- Patients on anticoagulation therapies may be at greater risk for postoperative complications such as hematomas that can result in paralysis
- Persistent pain at the neurostimulator site
- Placement of the epidural lead-extension is a surgical procedure that may expose patients to risks of epidural hemorrhage, hematoma, or paralysis
- Radicular chest wall stimulation
- Seroma or hematoma at the neurostimulator site
- Change in stimulation, possibly related to cellular changes around the electrode(s), shifts in electrode position, loose electrical connections, lead or extension fractures, which has been described by some patients as uncomfortable stimulation (jolting or shocking sensation).
- Formation of reactive tissue around the lead in the epidural space can result in delayed spinal cord compression and paralysis, requiring surgical intervention. Time to onset can range from weeks to many years after implant.
- Stimulation-dependent gastrointestinal symptoms such as nausea, diarrhea, incontinence, or constipation
- Stimulation-dependent bladder symptoms such as urinary retention, incontinence, or frequency
- Tissue damage at the implant site

11.2.2 Device/Software Deficiencies Risks

The use of SCS systems include risk of the following device deficiencies:

- Mechanical failure/damages of system components, e.g., lead fracture (increased impedance), or breach of insulation
- Migration or dislodgement of the lead(s)
- Programming and/or telemetry problems that might limit the capability to program or determine what parameters are programmed
- Automatic adjustment of output that might provide output that is below or above the desired values
- Outside electromagnetic interference (e.g., cardioversion, defibrillation, electrocautery etc.) might affect that output or programming of the system

11.2.3 Radiographic Risks

As part of the study, subjects may be required to have fluoroscopic or X-ray images taken of their device and/or leads that are additional to those required for commercial procedures. This represents a negligible amount of additive radiation exposure beyond imaging used as part of a standard trial lead placement. Winner⁴¹ found that the mean total fluoroscopy time for SCS trialing procedures (n = 110) averaged 133.4 s with a standard deviation of 84.8 s, with additional imaging required for implant of permanent leads and the INS. For example, five images are roughly the equivalent of 1.7 s of pulsed fluoroscopy at the lowest frame rate (3 pulses/s). This is much lower than the average time for the trialing procedure (at the most conservative estimate of 3 pulses/s) and under one-tenth of a standard deviation from the mean. Further, Schmid⁴² found that 1 min. of pulsed fluoroscopy at 3 pulses/s (180 images— far above what is anticipated for this study beyond commercial procedures) for fluoroscopy-guided perineural/epidural injections of the lumbar spine (a reasonable analog to the thoracic imaging performed as part of this study) results in an effective dose of 0.07 mSv and 0.08 mSv in males and females, respectively. Pradhan⁴³ reports that cancer risk can't be estimated from doses below 100 mSv.

11.3 Risk Minimization

The potential risks associated with Inceptiv system were identified and risk control measures were defined. Any potential risks associated with this study are further minimized by selecting qualified investigators and training study personnel on the CIP.

In addition, Investigators will be actively involved in the implantation and follow-up of the subjects implanted with the SCS systems.

Risks will be minimized by careful assessment of each subject prior to, during, and after implant of the SCS. Prior to implant, it is recommended subjects undergo a complete physical evaluation.

Medtronic has further minimized the possibility of risks by performing required laboratory and pre-clinical testing prior to the Closed-Loop SCS study, implementing quality control measures into production processes, providing guidelines for subject selection and evaluation, and providing adequate instructions and labeling.

After implantation, subjects in the Closed-Loop SCS study will be followed at regular intervals to monitor the condition of the implanted system and the battery. At each required visit, the Investigator must interrogate the SCS to verify appropriate function and to evaluate pacing and sensing characteristics and to assess any adverse events. Informed consent will include description for the subject to understand that the subject should inform any health care personnel before any medical procedure, that they have an implanted SCS system. Additionally, if the subject will undergo a cardioversion or defibrillation, with the implanted SCS system, ensure that stimulation is turned off for the duration of the medical procedure. Please refer to the Investigator's Brochure, Information for Prescribers or the Patient Therapy Guide for additional information.

11.4 Potential Benefits

The Inceptiv system may offer no benefit. The potential benefit of having the Inceptiv system, above and beyond SCS therapy for the treatment of chronic pain, is the reduction of overstimulation events, if the closed-loop feature is enabled. The information gained from this study could result in the improved management of other patients with chronic pain. Additionally, information collected from this study may assist in the design of new product(s)/therapy(ies).

11.5 Risk-Benefit Rationale

The benefit of the study lies in the knowledge to be gained from the results and the potential to improve SCS therapy. All potential risks have been controlled to a level as far as possible. Any residual risk is determined to be acceptable given the expected benefit.

12. Adverse Events and Device Deficiencies

12.1 Adverse Events

AE definitions are provided in Table 7. The following AEs will be collected throughout the study duration, starting at the time of signing the IC:

- procedure related
- device related
- therapy related
- serious adverse events regardless of relatedness

Reporting of these events to Medtronic will occur on an AE eCRF. Each event must be reported separately. Documented pre-existing conditions are not considered AEs unless the nature or severity of the condition has worsened. A subset of AEs will be collected in this study as these are the most relevant to the study device and study design given no new or increased risk with the Inceptiv system.

UAE, listed in Table 7, need not be reported unless the adverse event worsens or is present outside the stated timeframe post-implant.

For AEs that require immediate reporting (see Table 9), initial reporting may be done by phone, fax, or on the eCRF completing as much information as possible. The completed AE CRF must be submitted to Medtronic as soon as possible.

Any medication/treatment associated with the treatment of an AE must be reported

Subject deaths are also required to be reported. Refer to Section 12.6 for Subject Death collection and reporting requirements.

Events that are not reportable for this study are:

- Sensation of stimulation (paresthesia)
 - Sensation of stimulation (e.g., tingling, buzzing) will not be reported as this may occur as part of this therapy.
 - Sensation of stimulation brought by protocol-prescribed activities (i.e. coughing, laughing, Valsalva) if transient and reversed by the subject returning to a neutral position (anytime occurred).
 - Overstimulation: uncomfortable sensation of stimulation (intense tingling, shocking, jolting) brought by protocol-prescribed activities if transient and reversed by the subject returning to a neutral position (as defined in Section 14.4).

- Transient periods of sensation or stimulation events that are uncomfortable to the subject that do not result in an intervention or are relieved by change in body position or decreasing therapy intensity

NOTE: Extended periods of sensation or overstimulation events that are uncomfortable to the subject (e.g. tingling, shocking, jolting) that result in intervention (e.g. reprogramming, turning the device off) will be reported.

12.2 Device Deficiency

The device deficiency definition is provided in Table 7. Device deficiency information will be collected throughout the study and reported to Medtronic. Note that device deficiency that result in an AE to the subject should be captured as an AE only. Device deficiencies that led to increasing pain, but still below baseline pain levels should be reported as only a device deficiency, not an AE.

Device deficiency that did not lead to an AE but could have led to a SADE (i.e., if suitable action had not been taken, if intervention had not been made, or if the circumstances had been less fortunate) require immediate reporting (see Table 9).

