10.18 Unscheduled Visits

Unscheduled visits may occur if programming changes are required to correct programming errors, to reprogram for pain optimization, or for an AE. Whenever feasible, subjects should have their devices interrogated.

The following information is required to be collected during unscheduled visits:

- Reason for visit
- If applicable, collect data files via the clinician programmer tablet and securely send to Medtronic
- Fluoroscopy/x-ray, if necessary
- Pain medications changes
- AEs/device deficiencies

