10.20 System Modification

System modifications (e.g. lead or device revision, replacement, or explant) may occur in the study due to ineffective or loss of therapy, AEs, device deficiencies, or subject concerns that are not correctable by programming. In the event of a system modification, the visit schedule for the subject will remain unchanged. If the SCS device requires replacement, contact a member of the Medtronic study team as the decision to allow re-implant will be handled on a case-by-case basis. If the system is explanted, the explanted system will be returned to Medtronic. All explanted products should be returned to Medtronic for analysis when permissible by local laws and regulations. See Sections 7.10 and 7.11 for final product disposition details.

The following information is required to be collected during system modification visits:

- Changes to the implanted system
- Collect data files via the clinician programmer tablet and securely send to Medtronic
- Fluoroscopy/x-ray, if necessary
- Pain medications
- AEs/device deficiencies

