	
the device or procedures are applied to; the device or procedures have an effect on;
 
  the event follows a known response pattern to the device (if the response pattern is previously known);  the discontinuation of device application (or reduction of the level of activation/exposure) and reintroduction of its use (or increase of the level of activation/exposure), impact on the event (when clinically feasible);  other possible causes (e.g. an underlying or concurrent illness/ clinical condition or/and an effect of another device, drug or treatment) have been adequately ruled out;  harm to the subject is due to error in use;  the event depends on a false result given by the device used for diagnosis, when applicable; 
In order to establish the relatedness, not all the criteria listed above might be met at the same time, depending on the type of device/procedures and the event.

Seriousness	

Serious Adverse Event (SAE)
	
AE that led to any of the following:
 
 a) death, b) serious deterioration in the health of the subject, users or other persons as defined by one or more of the following: 
 1. A life-threatening illness or injury, or 2. A permanent impairment of a body structure or a body function, including chronic disease, or 3. In-patient or prolonged hospitalization, or 4. Medical or surgical intervention to prevent life-threatening illness or injury or permanent impairment to a body structure or a body function, c) fetal distress, fetal death or a congenital abnormality or birth defect including physical or mental impairment. 
Note 1: Planned hospitalization for pre-existing condition, or a procedure required by the CIP, without serious deterioration in health, is not considered an SAE. (ISO 14155:2020, 3.45)

Serious Adverse Device Effect (SADE)
	
Adverse device effect that has resulted in any of the consequences characteristic of a serious adverse event. (ISO 14155:2020, 3.44)

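### CIP 12.2 makes no exception for surgery or hospitalisation, so a device deficiency with pain still below baseline can be missing from the AE and SAE tables

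*Protocol*

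**What the plan says.** Section 12.2 of the protocol has three recording rules for device deficiencies (DDs).

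- A deficiency that causes an AE goes on the AE form alone: "Note that device deficiency that result in an AE to the subject should be captured as an AE only".
- A deficiency that raises pain, but not to baseline, goes the other way: "Device deficiencies that led to increasing pain, but still below baseline pain levels should be reported as only a device deficiency, not an AE".
- Immediate reporting applies to a "Device deficiency that did not lead to an AE but could have led to a SADE". Such an event is still handled as a deficiency.

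Section 11.2.2 lists lead failure among the deficiencies: "Mechanical failure/damages of system components, e.g., lead fracture (increased impedance), or breach of insulation". Section 10.20 foresees surgery: "System modifications (e.g. lead or device revision, replacement, or explant) may occur in the study due to ineffective or loss of therapy". The same sentence goes on to name AEs and device deficiencies as further, separate reasons.

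Section 12.1 requires collection of SAEs whether or not they are related. SAP 7.10 tabulates AEs with a count of serious events and promises a narrative for each serious device- or therapy-related AE. For deficiencies it gives only the number of deficiencies and the number and percentage of subjects.

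**The concern.** The second rule in 12.2 turns only on pain relative to baseline. What the deficiency led to plays no part. A subject whose lead fractures, who loses most of the benefit, and who is admitted for revision meets the wording as long as pain has not returned to the baseline level. The event is then a deficiency and nothing more.

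The SAP describes this as a first-in-man study of the fully implantable device. Its AE and SAE tables will be read as the device's safety record. A hardware failure that costs the subject a second operation is an event that readers will expect to find there.

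**Working it through.** The documents state no rate or count for this point, so there is no figure to reproduce. The check sets the passages side by side.

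1. **Can the event be an SAE?** Table 7 defines an SAE as an AE that led to a listed outcome. An event that 12.2 rules not to be an AE cannot reach that definition, even if the subject is hospitalised.

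2. **What is lost on the deficiency form?** The minimum content in 12.5 marks three items as applying to AEs only: seriousness and relatedness, treatment, and outcome with resolution date. The minimum for a deficiency is the date, a description, and the model and identifiers. The duty in 12.3 to follow to resolution is also written for AEs.

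3. **What reaches the tables?** Protocol 14.7 and SAP 7.10 break AEs down by seriousness. Neither splits deficiencies by seriousness, surgery or hospitalisation. A fracture corrected by revision and a telemetry fault each count as one deficiency.

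4. **Does other text settle it?** Section 12.1 collects all SAEs regardless of relatedness, which pulls against 12.2 when an admission follows. No sentence gives either precedence. Section 15.1 declares the study's departures from ISO 14155 event handling (only certain AE types, and no non-subject AEs); the 12.2 rule is not among them. For uncomfortable stimulation, the note in 12.1 makes intervention the trigger for reporting. Section 12.2 has no such trigger for pain.

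5. **Is any one table complete?** No. Under the first rule a lead failure that causes an AE appears only among AEs; under the second it appears only among deficiencies. Neither table alone counts all lead failures.

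6. **How wide is the band below baseline?** This is an illustration, not an estimate. The inputs are the baseline overall VAS floor of 60 mm for low-back and/or leg pain (9.3) and the 50% relief needed in the device trial before implant (10.11). I assume that exactly 50% relief persists on the permanent system and that pain is read in whole millimetres. For baseline B, pain on therapy is 0.5B and the highest value still below baseline is B − 1. The rise is (B − 1) − 0.5B, and the remaining relief is 1/B.
   - B = 60: 30 to 59 mm, rise 29 mm, remaining relief 1/60 = 1.7%.
   - B = 80 (assumed): 40 to 79 mm, rise 39 mm, remaining relief 1/80 = 1.25%.
   - B = 100 (assumed): 50 to 99 mm, rise 49 mm, remaining relief 1/100 = 1.0%.

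   Nearly all the benefit can go while the event stays under the deficiency-only rule.

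**The case against.** The strongest defence is that this is a pre-specified classification. Chronic pain is the pre-existing condition, and 12.1 does not treat such a condition as an AE unless it has worsened. Pain still below baseline has not worsened relative to entry. That is a plausible basis for the cut, although 12.2 does not state it, and it does not explain why a device-caused failure that leads to surgery should go without an AE assessment.

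Four stronger readings are tempting, and the documents do not support them.

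- **That the event disappears.** It does not. It is recorded and counted as a deficiency, sponsor staff review it (12.5.1, 13.2), and the change to the system is recorded under 10.20. If it could have become a SADE, it needs immediate reporting and a classification by investigator and sponsor (12.2, Table 8). Complications of the revision remain procedure-related AEs.
- **That every revision is a missed SAE.** Table 7 counts surgery only when it prevents life-threatening harm or permanent impairment. Note 1 excludes a planned admission for a pre-existing condition without serious deterioration in health. A day-case or planned revision might not qualify in any event.
- **That 12.2 contradicts the adverse-event list in 11.2.1.** The entry there reads "Loss of pain relief may return patients to their underlying pain condition". That describes a return to the original pain, whereas 12.2 covers pain still below it. The two can stand together.
- **That a number of missing events can be given.** The readable text has no rate of lead failure or revision. Section 10.20 also separates loss of therapy from device deficiency, and 12.2 covers only the latter, so a revision rate for lost therapy would be the wrong base.

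The instruction is also worded as a recommendation (should), so some sites may report an AE regardless. Inconsistent practice between sites would not make the counts easier to interpret.

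**Conclusion.** The gap is real and should be closed. Followed as written, 12.2 allows a deficiency that leads to surgical revision, replacement, explant or hospitalisation to stay out of the AE and SAE counts and the serious-event narratives, and it is not reconciled with 12.1. The rule can only move events out of the AE tables, so any effect on the reported AE/SAE rate is downward.

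Its size cannot be computed from the documents. It depends on how many deficiencies lead to surgery or admission with pain still below baseline, and on how many of those would satisfy Table 7. The conclusion rests on the readable text; a redacted section might hold a separate summary of system modifications. Safety is descriptive here, with no target or test, so no formal inference is affected.

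**What to change.** In 12.2, except from the deficiency-only rule any deficiency that leads to surgical revision, replacement, explant or hospitalisation. Record these as AEs whatever the pain level relative to baseline, assess them for seriousness and relatedness under Table 7, and link them to the deficiency record. The AE-only sentence in 12.2 needs a matching exception so that the deficiency record is kept. The change reconciles 12.2 with 12.1 for these events, and Table 7 still decides which of them are serious.

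In SAP 7.10, add one table of all deficiencies and AEs that led to system modification or hospitalisation, whichever form they were recorded on, with linked records counted once.

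I would not replace the baseline comparison with the subject's last pain score. The visible data lists for unscheduled and system-modification visits (10.18, 10.20) include no VAS, so that would need additional assessments.

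The cost is a short amendment to 12.2, a form instruction, one more table and a somewhat higher reported AE/SAE rate. Only recording and tabulation change; clinical management does not.

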12.3 Processing Updates and Resolution

For any changes in status of a previously reported adverse event or device deficiency (i.e. change in actions taken, change in outcome, change in relatedness), information needs to be updated on, or added to the original AE or device deficiency form. All AEs must be followed until the AE has been resolved, is unresolved with no further actions planned, the subject dies or exits the study, or until study closure, whichever occurs first.

In the event that a subject is exited from the study prior to study completion, all efforts should be made to continue following the subject until all ongoing device and/or procedure related AEs, as classified by the investigator, are resolved, unresolved with no further actions planned, or until official study closure, whichever occurs first. At the time of study exit, all collected AEs with an outcome of “not recovered/not resolved”, “recovering/resolving” or “unknown” must be reviewed and updates provided as applicable.

12.4 Definitions/Classifications

For the purposes of the clinical report, Medtronic will classify each adverse event according to ISO 14155:2020. Where the definition indicates “device”, it refers to any device used in the study. This might be the device under investigation, or any market released component of the system. It is the responsibility of the Investigator to identify the occurrence of all AEs and device deficiencies and to ensure the required information is accurately documented in the medical records and reported to Medtronic.

Table 7: Adverse Event and Device Deficiency Definitions

General	
Adverse Event (AE)	Untoward medical occurrence, unintended disease or injury, or untoward clinical signs (including abnormal laboratory findings) in subjects, users or other persons, whether or not related to the

Evaluation of Long-term Patient Experience with a Medtronic Closed-Loop SCS System (Closed-Loop SCS study)

Clinical Investigation Plan

06JAN2023

Version 4.0

Page 59 of 117

Medtronic

	
investigational medical device and whether anticipated or unanticipated.
 
Note 1: This definition includes events related to the investigational medical device or the comparator.
 
Note 2: This definition includes events related to the procedures involved.
 
Note 3: For users or other persons, this definition is restricted to events related to investigational medical devices.
 
(ISO 14155:2020, 3.2)

Adverse Device Effect (ADE)	
AE related to the use of an investigational medical device.
 
Note 1: This definition includes AEs resulting from insufficient or inadequate instructions for use, deployment, implantation, installation, or operation, or any malfunction of the investigational medical device.
 
Note 2: This definition includes any event resulting from an use error or from intentional misuse of the investigational medical device.
 
Note 3: this includes 'comparator' if the comparator is a medical device
 
(ISO 14155:2020, 3.1)

Device Deficiency	
Inadequacy of a medical device with respect to its identity, quality, durability, reliability, usability, safety or performance.
 
Note 1: DD include malfunctions, use errors and inadequacy in the information supplied by the manufacturer including labeling.
 
Note2: This definition includes device deficiencies related to the investigational medical device or the comparator. (ISO 14155:2020, 3.19)

Relatedness	
Device related (Those classified as Investigational in Table 3)	
An adverse event that results from the presence or performance (intended or otherwise) of the Investigational components of Inceptiv system.
 
 • Inceptiv INS • Vectris SureScan MRI leads • Specify SureScan MRI 5-6-5 leads • Clinician Tablet • Clinician Programmer Application • Stimulation Trialing Clinician Programmer Application • Programmer Platform Software-Communication Manager Application • Patient Data Service Application • Patient Handset • Patient Programmer Application • Patient Programmer Trialing Application • Patient Telemetry Communicator

Evaluation of Long-term Patient Experience with a Medtronic Closed-Loop SCS System (Closed-Loop SCS study)

Clinical Investigation Plan

06JAN2023

Version 4.0

Page 60 of 117

Medtronic

	
 • Recharger Application • Recharger
Procedure Related	An adverse event that occurs due to any procedure related to the trial, implant, explant or surgical modification of the Inceptiv system or any of the Inceptiv system components.
Therapy Related	An adverse event that occurs due to the therapy delivered by the Inceptiv system, should not include events that resulted from a malfunction of the device (i.e. hardware-related events).
Not Related	
Relationship to the device or procedures can be excluded when:
 
  the event has no temporal relationship with the use of the device or procedure  the event does not follow a known response pattern to the device (if the response pattern is previously known) and is biologically implausible;  the discontinuation of device application or the reduction of the level of activation/exposure - when clinically feasible – and reintroduction of its use (or increase of the level of activation/exposure), do not impact on the event;  the event involves a body-site or an organ not expected to be affected by the device or procedure;  the event can be attributed to another cause (e.g. an underlying or concurrent illness/ clinical condition, an effect of another device, drug, treatment or other risk factors);  the event does not depend on a false result given by the device used for diagnosis, when applicable; 
In order to establish the non-relatedness, not all the criteria listed above might be met at the same time, depending on the type of device/procedures and the serious event

Possible	The relationship is weak but cannot be ruled out completely. Alternative causes are also possible (e.g. an underlying or concurrent illness/ clinical condition or/and an effect of another device, drug or treatment). Cases where relatedness cannot be assessed or no information has been obtained should also be classified as possible.
Probable	The relationship seems relevant and/or the event cannot reasonably be explained by another cause.
Causal relationship	
The event is associated with the device or study procedures beyond reasonable doubt when:
 
  the event is a known side effect of the product category the device belongs to or of similar devices and procedures;  the event has a temporal relationship with device use/application or procedures;  the event involves a body-site or organ that

Evaluation of Long-term Patient Experience with a Medtronic Closed-Loop SCS System (Closed-Loop SCS study)

Clinical Investigation Plan

06JAN2023

Version 4.0

Page 61 of 117

Medtronic

	
the device or procedures are applied to; the device or procedures have an effect on;
 
  the event follows a known response pattern to the device (if the response pattern is previously known);  the discontinuation of device application (or reduction of the level of activation/exposure) and reintroduction of its use (or increase of the level of activation/exposure), impact on the event (when clinically feasible);  other possible causes (e.g. an underlying or concurrent illness/ clinical condition or/and an effect of another device, drug or treatment) have been adequately ruled out;  harm to the subject is due to error in use;  the event depends on a false result given by the device used for diagnosis, when applicable; 
In order to establish the relatedness, not all the criteria listed above might be met at the same time, depending on the type of device/procedures and the event.

Seriousness	

Serious Adverse Event (SAE)
	
AE that led to any of the following:
 
 a) death, b) serious deterioration in the health of the subject, users or other persons as defined by one or more of the following: 
 1. A life-threatening illness or injury, or 2. A permanent impairment of a body structure or a body function, including chronic disease, or 3. In-patient or prolonged hospitalization, or 4. Medical or surgical intervention to prevent life-threatening illness or injury or permanent impairment to a body structure or a body function, c) fetal distress, fetal death or a congenital abnormality or birth defect including physical or mental impairment. 
Note 1: Planned hospitalization for pre-existing condition, or a procedure required by the CIP, without serious deterioration in health, is not considered an SAE. (ISO 14155:2020, 3.45)

Serious Adverse Device Effect (SADE)
	
Adverse device effect that has resulted in any of the consequences characteristic of a serious adverse event. (ISO 14155:2020, 3.44)


Unanticipated Serious Adverse Device Effect (USADE)
	
Serious adverse device effect which by its nature, incidence, severity or outcome has not been identified in the current version of the risk assessment. Note 1: Anticipated serious adverse device effect (ASADE) is an effect which by nature, incidence, severity or outcome has been identified in the risk assessment.

Evaluation of Long-term Patient Experience with a Medtronic Closed-Loop SCS System (Closed-Loop SCS study)

Clinical Investigation Plan

06JAN2023

Version 4.0

Page 62 of 117

Medtronic

	(ISO14155:2020 3.51)														
Significant Safety Issue (SSI)	
A safety issue that could adversely affect the safety of participants or materially impact on the continued ethical acceptability or conduct of the trial.
 
(NHMRC Safety monitoring and reporting in clinical trials involving therapeutic goods November 2016)
														
Urgent Safety Measure (USM)	
A measure required to be taken in order to eliminate an immediate hazard to a participant’s health or safety.
 
Note: This type of significant safety issue can be instigated by either the investigator or sponsor and can be implemented before seeking approval from ECs or institutions.
 
(NHMRC Safety monitoring and reporting in clinical trials involving therapeutic goods November 2016)
														
Serious Health Threat	
Signal from any adverse event or device deficiency that indicates an imminent risk of death or a serious deterioration in the health in subjects, users or other persons, and that requires prompt remedial action for other subjects, users or other persons
 
NOTE 1: This would include events that are of significant and unexpected nature such that they become alarming as a potential serious health hazard or possibility of multiple deaths occurring at short intervals.
 
(ISO 14155:2020, 3.46)
														
Unavoidable Adverse Events (UAE)	
An Adverse Event inherent to a surgical procedure that is expected to occur in all subjects for a projected duration according to the Investigator’s opinion.
 
Unavoidable AEs are not considered reportable unless the AE worsens or is present outside the stated timeframe.
 
Including, but not limited to:
 
  
 Description	Timeframe (hours) from the Surgical Procedure	
   
 Anesthesia related nausea / vomiting	24	
 
 Low-grade fever (<100°F or <37.8°C)	48	
 
 Pain at the access site	72	
 
 Mild to moderate bruising / ecchymosis	168	
 
 Sleep problems (insomnia)	72	
 
 Back pain related to lying on table	72	
  
	Description	Timeframe (hours) from the Surgical Procedure	Anesthesia related nausea / vomiting	24	Low-grade fever (<100°F or <37.8°C)	48	Pain at the access site	72	Mild to moderate bruising / ecchymosis	168	Sleep problems (insomnia)	72	Back pain related to lying on table	72
Description	Timeframe (hours) from the Surgical Procedure														
Anesthesia related nausea / vomiting	24														
Low-grade fever (<100°F or <37.8°C)	48														
Pain at the access site	72														
Mild to moderate bruising / ecchymosis	168														
Sleep problems (insomnia)	72														
Back pain related to lying on table	72														

